9.3.3. Covariates

9.3.3.1. Baseline Patient Characteristics

The following characteristics will be captured at baseline – the data point closest to the index date will be used:

- **Index date:** The month and year of the patient's index date (start of 1L treatment) will be identified and reported:
 - January, February, March, April, May, June, July, August, September, October, November, December
 - 2018, 2019, 2020, 2021, 2022
- **Age:** Age (in years) as of index date will be reported as a numeric value and categorised as follows:
 - ≥ 18 years and < 30 years, ≥ 30 years and < 40 years, ≥ 40 years and < 50 years, ≥ 50 years and < 60 years, ≥ 60 years and < 70 years, ≥ 70 years and < 80 years, or ≥ 80 years
- **Biological Sex:** *Male or female*; patients with sex stated as unknown will be classified as missing data for the purpose of this analysis.
- **Body Mass Index (BMI):** Weight in kilograms divided by height in meters squared, will be utilised as either a continuous variable or a categorical variable using the following categories: Underweight (Below 18.5), Normal (18.5 - 24.9), Overweight (25.0 - 29.9), Obese (30.0 – 34.9) and Morbidly obese (35.0 and greater). Most recent measurement prior to and including index date will be reported. If BMI is provided explicitly, patients will be categorised into these groups if and where appropriate.

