Each data source is likely to capture a large proportion of GO-treated patients in that country, hence their selection. The Austrian, Belgian and German centres have been selected as they meet the feasibility requirements (capture the relevant data variables) and due to the sample size of GO patients that they contain. The Austrian Myeloid Registry recruits data on patients with myeloid diseases from 15 Austrian centres (excluding the Medical University of Vienna) with an estimated enrollment of 3000 patients. The eligibility criteria below are largely based upon the recommend use of GO; ensuring that the overall patient sample gathered will be clinically representative of the GO treated population.

The initiation date of 1L treatment within the indexing period will be defined as the index date. De novo AML diagnosis will be captured within the screening questions of the eCRF and fully defined for each data source within the Statistical Analysis Plan (SAP). Baseline patient demographics and clinical characteristics will be evaluated at index. Treatment patterns and effectiveness outcomes will be described throughout the follow-up period. Patients will have a minimum follow-up of 3 months defined as patients with 3 months of data, following the 1L treatment initiation. This will allow for assessment of treatment patterns and early effectiveness outcomes. Follow-up will end with the following endpoints: death, loss of data (eg, transfer to a new hospital) or end of the study period. In order to maximise the follow-up data captured necessary to accurately assess survival outcomes (EFS, RFS and OS), follow-up will extend up until either the last data available for the patient (in Austrian, Belgium, and German sites), or the date of database extraction (in the Austrian Myeloid Registry). Patients who have limited follow-up data which is not sufficient for the assessment of OS and accurate EFS and RFS, will be right-censored for the purpose of survival outcome specific analysis. Patients who die within the 3-month follow-up period would be considered eligible for inclusion in order to evaluate EFS, RFS and OS outcomes.

Figure 1. Study Schematic

Study Schematic–eCRF and secondary data dataset design

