9.2.1. Inclusion Criteria

Patients must meet all of the following inclusion criteria to be eligible for inclusion in the study:

1. Patient has a clinical diagnosis of **de novo** AML.
2. Patient is aged 18 years or older.
3. Patient has a cytogenetic risk stratification of 'favourable' or 'intermediate (classified according to the International System for Human Cytogenic Nomenclature criteria.¹³

4. Patient has been treated with GO in a 1L induction setting in a combination chemotherapy treatment.
5. Patient has data points available for a minimum of 3 months data from the first GO-containing regimen (index). Patients who die within the 3 months are eligible for inclusion within the study.
6. *For patients from Austrian, Belgium, and German sites:* Evidence of a personally signed and dated informed consent document indicating that the patient (or a legally acceptable representative) has been informed of all pertinent aspects of the study.
Note – may not be required and depends on individual country/site IRB guidance.

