9.3.3.2. Baseline Clinical Characteristics

- **Date of diagnosis:** day, month, and year of AML diagnosis will be captured.
- **Comorbidities:** The presence of specific comorbidities prior to the index date (ie, not constrained by the study period) will be reported for all patients based on the presence of diagnosis codes (ICD-10). The list of comorbidities captured are as follows:
 - *Myocardial infarction, congestive heart failure, peripheral vascular disease / peripheral arterial disease, stroke, dementia, chronic obstructive pulmonary disease (COPD), connective tissue disease, peptic ulcer disease, liver disease, diabetes, hemiplegia, moderate-to-severe chronic kidney disease, solid tumour, lymphoma, aids, hepatitis B, hepatitis C, other, don't know, or no concomitant conditions*
- **Qual-Charlson Comorbidity Index:** The CCI prior to the index date will be calculated based on the presence of specific diagnosis (ICD-10) codes and scored using published weights for each condition included .¹⁴
- **ELN 2017 risk group:** The ELN risk group (*Favourable or Intermediate*) will be reported as a continuous categorical variable
- **ISCN karyotype**
- **Classical cytogenetics:** will be reported as a continuous categorical variable:
 - *Normal; Clonal changes; Non-clonal changes; Both Clonal and non-clonal changes; Unknown; No mitoses*
- **Number of metaphases analysed:** reported as a continuous numerical and categorical variable.
- **Number of abnormal metaphases:** reported as a continuous numerical and categorical variable.
- **Number of clonal changes:** reported as a continuous numerical and categorical variable.
- **Number of non-clonal changes:** reported as a continuous numerical and categorical variable.

- **WHO specific recurrent changes:** reported as a categorical variable
 - *Normal; t (8; 21) (q22; q22) AML1-ETO; inv (16) (p13; q22) CBFβ- / MYH11; t (15; 17) (q22; q12) PML-RARA; t (1; 19) (q23; p13) E2A-PBX1; t (4; 11) (q21; q23) MLL-AF4; t (12; 21) (p13; q22) TEL-AML1; t (9; 22) (q34; q11) BCR-ABL; part (1) (p32; q32) SIL-TAL1 9; Not performed/unknown*
- **ECOG/WHO performance status:** the performance status at the time closest to index will be reported as a categorical variable:
 - *0 – Fully active, able to carry on all pre-disease performance without restriction;*
 - *1 – Restricted in physically strenuous activity but ambulatory and able to carry out work of a light or sedentary nature, eg, light house work, office work;*

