 - *2 – Ambulatory and capable of all selfcare but unable to carry out any work activities. Up and about more than 50% of waking hours;*
 - *3 – Capable of only limited selfcare, confined to bed or chair more than 50% of waking hours;*
 - *4 – Completely disabled. Cannot carry on any selfcare. Totally confined to bed or chair;*
- **Level of leucocytes [m/L]:** Captured at the time closest to index will be reported as a continuous numerical variable.
- **Level of thrombocytes [m/L]:** Captured at the time closest to index will be reported as a continuous numerical variable.
- **Level of lactate dehydrogenase (LDH) [U/L]:** Captured at the time closest to index will be reported as a continuous numerical variable.
- **Bone marrow blasts [%]:** Captured at the time closest to index will be reported as a continuous numerical variable.
- **Peripheral blood marrow blasts [%]:** Captured at the time closest to index will be reported as a continuous numerical variable.

Categories for variables will be further defined upon receipt of data within the SAP.

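### Six treatment-sensitive baseline variables are taken as the value closest to index with no limit to pre-treatment values, so an on-treatment value can be reported as baseline

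*Protocol*

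**What the plan says.** Section 9.2 sets the anchor: "The initiation date of 1L treatment within the indexing period will be defined as the index date". Section 9.3.3.1 begins its list (index date, age, sex, BMI) with the general statement that "the data point closest to the index date will be used".

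The text that matters here is in section 9.3.3.2, where each variable has its own timing rule. For ECOG/WHO status, "the performance status at the time closest to index will be reported as a categorical variable". Leucocytes, thrombocytes, LDH, bone marrow blasts and peripheral blasts each carry the sentence "Captured at the time closest to index will be reported as a continuous numerical variable". None of these six entries says before or after, and none gives a window.

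Other baseline variables are treated differently. For BMI, section 9.3.3.1 says "Most recent measurement prior to and including index date will be reported". For comorbidities, section 9.3.3.2 reports "The presence of specific comorbidities prior to the index date", and for the comorbidity score, "The CCI prior to the index date will be calculated".

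At the end of section 9.3.3.2 the protocol leaves the categories of variables to the SAP. It does not mention the timing of measurements there.

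**The concern.** Induction treatment is given to change blasts and leucocytes, and it can affect thrombocytes, LDH and performance status within days. A baseline rule for such variables has to keep out values measured under treatment. Here the one-sided rules are used for BMI and comorbidity, which change little over a few days, and the rule without a direction is used for the variables that treatment moves.

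Three things are at stake.

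- Section 8 makes the description of clinical characteristics a co-primary objective.
- Section 9.9 relies on those characteristics, compared with published datasets, to judge how far site selection and consent have biased the sample. That comparison weakens if some values were measured on treatment.
- Six data sources are pooled. How often an on-treatment value is the nearest one depends on local sampling habits, so the rule could produce differences between sources that are not differences between patients.

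**Working it through.** There is no stated figure to reproduce. The check is to set each timing rule against the definition of index.

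| Variable | Protocol section | Timing rule | On-treatment value excluded? |
|---|---|---|---|
| BMI | 9.3.3.1 | latest on or before index | yes, apart from day-of-index values |
| Comorbidities | 9.3.3.2 | before index | yes |
| Charlson index | 9.3.3.2 | before index | yes |
| ECOG/WHO status | 9.3.3.2 | closest to index | no |
| Leucocytes, thrombocytes, LDH | 9.3.3.2 | closest to index | no |
| Bone marrow and peripheral blasts | 9.3.3.2 | closest to index | no |

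**When the rule selects an on-treatment value.** Let the last pre-treatment value be *a* days before index and the first later value *b* days after it. The closest-to-index rule selects the later value whenever *b* < *a*. With assumed days *a* = 7 and *b* = 3, it takes the day +3 value, while the BMI rule would take the day −7 value.

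**Where it cannot bite.** Counting in whole days, *b* is at least 1.

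- If *a* = 0, the day-of-index value is chosen under either rule.
- If *a* = 1, a later value can at most tie (*b* = 1), and the protocol does not say how a tie is resolved.
- Displacement is therefore certain only when *a* is 2 or more and *b* is smaller than *a*.

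**What happens on day 0.** A same-day value may come before or after the first dose. In addition, section 9.3.2.1 measures the time between the start of chemotherapy and the start of GO, so a value shortly after index may follow one drug and precede the other.

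**Size.** The shift in a reported mean is the share of patients affected multiplied by their mean change between the two measurements. The protocol gives neither factor. It states no sampling schedule and no interval from diagnosis to treatment.

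**Scope for later repair.** Table 1 gives 50 + 30 + 50 + 42 + 18 + 40 = 230 expected patients. The 40 German patients (40/230 = 17%) are to be fully anonymised, and sections 9.6 and 9.8 say that queries needing re-identification cannot be made for them. If only the closest value is entered for those patients, the site cannot later be asked for the earlier one.

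**The case against.** The strongest reply is that the protocol never says before or after. The entries sit under a baseline heading, and section 9.2 separates characteristics assessed at index from patterns and outcomes described over follow-up. Abstractors may well use diagnostic values anyway. Sections 9.3 and 9.7 leave final variables and detailed methods to a SAP that is not at hand, and a baseline window is often set there.

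Part of this stands. The rule permits on-treatment values and does not call for them, and same-day or day-before blood counts would reduce the effect. But the protocol does state a rule for each of the six variables, and read plainly it selects the nearer value whichever side of index it falls on. A SAP that followed it would inherit the problem.

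A reader might also infer three stronger things that the protocol does not support.

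- *Disease burden would be understated throughout.* That is probable for blasts and leucocytes. Thrombocytes, LDH and performance status could move either way early in induction.
- *Outcome results stratified by these variables would be distorted.* No such stratification is planned. The possible subgroups in sections 9.7 and 9.9 concern data source, regimen or dosing schedule, risk group and availability of MRD. The ENCePP checklist answers no on stratified analyses, and section 9.9 says there are no statistical comparisons.
- *The error has a calculable size.* Any percentage-point figure would only be the product of two assumed inputs.

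It is also fair to say that pre-index values are not always untreated. Exclusion criterion 1 allows leukoreduction with or without hydroxyurea before GO, so a pre-index leucocyte count may already be lowered.

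**Conclusion.** The point holds on the text. For six variables that induction treatment can change, section 9.3.3.2 fixes a timing rule that admits on-treatment values as baseline, and this is inconsistent with the rules for BMI, comorbidities and the Charlson index. The effect is confined to the baseline description and its comparison with published data. That description is a co-primary result, so the wording should be corrected.

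The frequency and size of the error are unknown, and its direction varies by variable. The conclusion rests on two conditions: that the rule is applied as written, and that some patients have a later value nearer to index than their last pre-treatment value. It does not depend on any assumed frequency.

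**What to change.** For the six variables in section 9.3.3.2, replace the closest-to-index wording with the most recent value on or before the index date, as already used for BMI. The general sentence in section 9.3.3.1 should be aligned with it. Add three provisions:

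- Treat a day-of-index value as baseline unless it is recorded as taken after the first first-line dose. This avoids depending on clock times, which the protocol does not mention.
- Count a patient with no qualifying value as missing for that variable. Section 9.7 already provides for reporting missing values.
- Where leukoreduction or hydroxyurea was given before index, flag that the leucocyte count may already be lowered.

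The work is a short change of wording and a date check in the eCRF, best made before data entry because of the limits on German queries. The cost is some more missing baseline values. There may be more of these in the registry (an estimated 30 of 230 patients, 13%), because section 9.3 says its variables are not all known and measurement dates may be unavailable.

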9.3.3.2. Baseline Clinical Characteristics

- **Date of diagnosis:** day, month, and year of AML diagnosis will be captured.
- **Comorbidities:** The presence of specific comorbidities prior to the index date (ie, not constrained by the study period) will be reported for all patients based on the presence of diagnosis codes (ICD-10). The list of comorbidities captured are as follows:
 - *Myocardial infarction, congestive heart failure, peripheral vascular disease / peripheral arterial disease, stroke, dementia, chronic obstructive pulmonary disease (COPD), connective tissue disease, peptic ulcer disease, liver disease, diabetes, hemiplegia, moderate-to-severe chronic kidney disease, solid tumour, lymphoma, aids, hepatitis B, hepatitis C, other, don't know, or no concomitant conditions*
- **Qual-Charlson Comorbidity Index:** The CCI prior to the index date will be calculated based on the presence of specific diagnosis (ICD-10) codes and scored using published weights for each condition included .¹⁴
- **ELN 2017 risk group:** The ELN risk group (*Favourable or Intermediate*) will be reported as a continuous categorical variable
- **ISCN karyotype**
- **Classical cytogenetics:** will be reported as a continuous categorical variable:
 - *Normal; Clonal changes; Non-clonal changes; Both Clonal and non-clonal changes; Unknown; No mitoses*
- **Number of metaphases analysed:** reported as a continuous numerical and categorical variable.
- **Number of abnormal metaphases:** reported as a continuous numerical and categorical variable.
- **Number of clonal changes:** reported as a continuous numerical and categorical variable.
- **Number of non-clonal changes:** reported as a continuous numerical and categorical variable.

- **WHO specific recurrent changes:** reported as a categorical variable
 - *Normal; t (8; 21) (q22; q22) AML1-ETO; inv (16) (p13; q22) CBFβ- / MYH11; t (15; 17) (q22; q12) PML-RARA; t (1; 19) (q23; p13) E2A-PBX1; t (4; 11) (q21; q23) MLL-AF4; t (12; 21) (p13; q22) TEL-AML1; t (9; 22) (q34; q11) BCR-ABL; part (1) (p32; q32) SIL-TAL1 9; Not performed/unknown*
- **ECOG/WHO performance status:** the performance status at the time closest to index will be reported as a categorical variable:
 - *0 – Fully active, able to carry on all pre-disease performance without restriction;*
 - *1 – Restricted in physically strenuous activity but ambulatory and able to carry out work of a light or sedentary nature, eg, light house work, office work;*
 - *2 – Ambulatory and capable of all selfcare but unable to carry out any work activities. Up and about more than 50% of waking hours;*
 - *3 – Capable of only limited selfcare, confined to bed or chair more than 50% of waking hours;*
 - *4 – Completely disabled. Cannot carry on any selfcare. Totally confined to bed or chair;*
- **Level of leucocytes [m/L]:** Captured at the time closest to index will be reported as a continuous numerical variable.
- **Level of thrombocytes [m/L]:** Captured at the time closest to index will be reported as a continuous numerical variable.
- **Level of lactate dehydrogenase (LDH) [U/L]:** Captured at the time closest to index will be reported as a continuous numerical variable.
- **Bone marrow blasts [%]:** Captured at the time closest to index will be reported as a continuous numerical variable.
- **Peripheral blood marrow blasts [%]:** Captured at the time closest to index will be reported as a continuous numerical variable.

Categories for variables will be further defined upon receipt of data within the SAP.

9.4. Data Sources

As indicated in [Section 9.1](#), all countries and data sources specified below are provisional and subject to final feasibility confirmation.

The primary investigators for each country involved in this study are as follows (inclusion of each provisional site is dependent on contractual agreement):

- Austria – [name], Medical University of Vienna
- Austria – [name], Chariman of the Austrian Group of Medical Tumor Therapy (AGMT)
- Belgium – [name], UZ Leuven; [name], Az Sint Jan Brugge; [name], Az Sint Jan Brugge; [name] [name], UZ Brussel
- Cologne – [name] [name], University of Cologne

Austrian, Belgian, and German centres

For Austrian, Belgian, and German centres, an eCRF will be used by physicians at study sites to abstract data for patients who meet the eligibility criteria outlined in [Section 9.2.1](#) and [Section 9.2.2](#). Sites will be selected based on the results of a site feasibility assessment.

Each eligible site will be required to complete a short screener for each patient, before abstracting data from electronic medical records (EMR) into the eCRF, to confirm their eligibility for the retrospective chart review. Sites will be instructed to refer to the patient's complete EMR whilst completing the eCRF and not to answer any question from memory or that is not listed within the patients' EMR.

The data to be abstracted will include, but is not limited to, baseline demographics and clinical characteristics, treatment patterns and effectiveness outcomes as detailed in [Section 9.3](#). Once the data are extracted, they will be stored in a secure study database. Further details around the data management can be found in [Section 9.6](#).

Austrian Myeloid Registry

The Austrian Myeloid Registry aims to assess the treatment patterns, clinical outcomes and quality of life of patients with myeloid diseases from 15 Austrian sites.¹⁵ Data will be extracted for patients who meet the eligibility criteria outlined in [Section 9.2.1](#) and [9.2.2](#), resulting in an estimated 30 patients. The data to be abstracted or extracted will include but is not limited to baseline demographics and clinical characteristics, treatment patterns and effectiveness outcomes. Where required, treatment patterns and effectiveness outcomes will be defined using numerical and statistical methods. Initial feasibility investigations showed the registry extract data in a similar way to an eCRF and extract data from EMRs at multiple sites across Austria.

It is estimated that around 230 patients will be included across Austria, Belgium, and Germany; this comprises of 1 site plus 1 registry in Austria, 3 sites in Belgium and 1 site in Germany. However, the final number will vary from this estimate and that is permissible.

9.5. Study Size

This study is purely descriptive and there will be no limit on the sample size in terms of patients meeting the eligibility criteria in [Section 9.2.1](#) and [9.2.2](#). Estimated sample sizes are presented below by county in Table 1. Sample sizes will be maximized where feasible and appropriate and will likely vary from the below estimates.

Table 1. Sample Size Estimations per Data Source

	Site name	Number of patients treated with GO
Austria	Medical University of Vienna	50
	Austrian Myeloid Registry	30
Belgium	UZ Leuven	50
	Az Sint Jan Brugge	42
	UZ Brussels	18
Germany	University of Cologne	40

9.6. Data Management

eCRF

Each patient enrolled into the study will have a unique identification number which will allow the study data to be pseudonymised. The linkage between the identification number and the patient will not be shared externally and sites will be required to permanently delete any linkage information following site close-out at the end of the study. In Germany, where subjects must be completely anonymised in order for their data to be processed without informed consent, these patients will not be assigned a unique identification number. Data will be abstracted by site staff from patient medical records and entered into an eCRF hosted on secure, password protected electronic data capture (EDC) software. The software has been certified as being compliant with the FDA's 21eCRF Part 11 regulation. Patient data will be entered into the eCRF identified only by the unique, anonymised identification number (except in Germany).

With the exception of Germany (where it will not be possible to identify patients' data after being entered), any inconsistencies noted in the eCRF data will be queried with the site using data clarification procedures. Automatic checks and prompts are also built into the EDC programme (eg, checks for out-of-range numeric values). Each individual eCRF will be further evaluated for logical consistency between study variables, potential outliers, and missing information. Sites will be queried for clarification via the EDC system if any such issues are identified. A full audit trail will be maintained against original data entries and, if

applicable, subsequent edits. Database lock will be issued when all queries have been resolved. Full details of the data management will be outlined in a data management plan.

Secondary datasets

For secondary data, anonymised data will be provided to the ARW Data and Analytics Team via an accredited Secure File Transfer System (SFTS) email and file encryption service or equivalent. Data will be securely stored on the central servers at ARW headquarters and access restricted to only the immediate project team.

Upon receipt of the data, ARW will assess the data quality and perform any required data cleaning and quality checking to address any erroneous or implausible observations in the data (which will be queried to resolution with the data custodians where appropriate). Quality checks will be logged, thus ensuring replicability and transparency of decisions for inclusion in external communications.

Inclusion and exclusion criteria (as per [Section 9.2](#)) will be applied to identify the target patient population and a flow diagram constructed to highlight patient attrition per selection criteria. Variables that require derivation from pre-existing data fields and code lists will be derived and data will be manipulated and transformed to construct a patient-level data frame on which all statistical analysis will be performed. All data manipulation, variable derivations and data analysis will be conducted in Stata v17.0 or the latest available version at time of data receipt (StataCorp, College Station, TX),¹⁶ and logged in coding files within the study folder to ensure replicability. See [Section 9.8](#) for quality control procedures.

All data collected for the study should be recorded accurately, promptly, and legibly. The investigator or qualified designee is responsible for recording and verifying the accuracy of subject data. By signing this protocol, the investigator acknowledges that his/her electronic signature is the legally binding equivalent of a written signature. By entering his/her electronic signature, the investigator confirms that all recorded data have been verified as accurate.

If this study has been outsourced, the institutional policies of the supplier should be followed for development of data management plans. However, the supplier should ensure compliance with Good Pharmacoepidemiology Practice, and all applicable federal, state, and local laws, rules and regulations relating to the conduct of the study.

Combined data

Where possible, variables across the eCRF and secondary datasets will be harmonized (as detailed in the SAP), as the initial feasibility investigations showed the registry extract data in a similar way to an eCRF this is believed to be possible for the majority of variables collected. If specific data variables must be requested from the Austrian Myeloid Registry, these will be aligned with the eCRF. Following alignment of common variables and cross-

referencing of eCRF responses, where possible, data from all sources will be combined in a single dataset – the method/process of this will be described in detail in the SAP.

